10.3.3.2. Secondary Analyses

10.3.3.2.1. Analyses on Secondary Efficacy Endpoints

In addition to the primary efficacy analysis of HbA1c, the following secondary efficacy outcomes will be analyzed on the mITT population:

- Body weight change from baseline to 3 months
- Percentage of patients reaching the HbA1c target of $\leq 7.0\%$
- Change from baseline of FBG at 3 months

- Change from baseline of waist circumference at 3 months.

The secondary continuous efficacy measures (change from baseline in body weight, waist circumference, and FBG) will also be analyzed using the MMRM models described above (with censoring data collected after initiation of rescue intervention). The MMRM model will include the model terms given for the previously described primary analysis model except the baseline of the corresponding variable replacing the baseline of HbA1c, and with the addition of the HbA1c strata (<8.5% or ≥8.5%). Baseline BMI category will be dropped from the analysis models for body weight change from baseline.

The percentage of patients reaching the HbA1c target of ≤7.0% at 3 months will be analyzed using a logistic regression analysis with fixed effects of treatment and stratification factors, and baseline as a covariate.

In addition to change from baseline in weight and waist circumference, change from baseline in BMI will be listed and summarized.

Descriptive statistics for each outcome will be presented by treatment group. For continuous variables, the descriptive statistics will include sample size, LS means, LS means standard error, mean, SD, median, minimum, and maximum. For categorical variables, the descriptive statistics will include sample size, frequency, and percentage.

10.3.3.3. Exploratory Analyses

The change from baseline of 7-point SMBG profiles will be analyzed using analysis of covariance model (ANCOVA) with treatment, baseline strata (metformin category, BMI category, and HbA1C category) as fixed effects, and the corresponding baseline as covariate.

10.3.4. Safety Analyses

10.3.4.1. Clinical Evaluation of Safety

The safety population will be used for safety analyses.

Safety measures will include vital signs, body weight, TEAEs (including SAEs and AESIs), and laboratory measures (including anti-LY3298176 antibodies). Summary statistics will be presented by treatment for the safety measures.

The summary statistics for continuous variables will be sample size, mean, SD, median, minimum, and maximum.

The summary statistics for categorical variables will be sample size, frequency, and percentage.

Exposure to each therapy during the treatment period of the study will be calculated for each patient and summarized by treatment group.

In addition, percent of patients requiring rescue therapy will be summarized.

Additional analysis, such as concentration–safety lab plots, may be performed if warranted upon review of the data.

10.3.4.2. Adverse Events

Adverse events will be listed by patient, actual term, preferred term, severity, and relationship to the treatment. Adverse events will be summarized as TEAEs (defined as events that are newly reported after randomization or reported to worsen in severity from baseline). The incidence of patients with at least 1 TEAE and the incidence of TEAEs by preferred term and system organ class will be presented by treatment group. The frequency and percentage of TEAEs will be presented. The incidence of patients with at least 1 TEAE assessed as possibly related to the investigational drug will be summarized by treatment group, in addition to the incidence of these possibly related TEAEs by preferred term. In addition, a summary of TEAEs by severity will be presented descriptively by treatment group.

Reported thyroid and adjudicated CV and pancreatic-related AEs will be listed by patient, and if there are a sufficient number of cases, they may be summarized by treatment group.

All SAEs will be listed by patient. If a sufficient number of SAEs are reported, incidence summaries similar to incidence of TEAEs will be included.

Discontinuations due to TEAEs will be listed by patient and summarized by treatment group.

10.3.4.3. Vital Signs

All vital signs will be listed using all randomized patients.

Descriptive statistics for the actual measurements and changes from baseline for systolic and diastolic BP and PR will be presented by treatment arm and visit. Corresponding figures may be presented.

Vital signs will be analyzed using a similar MMRM-based model as for the primary analysis.

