Week of Treatment	-2	-1	0	1	2	4	4	8	8	12	(15)	
Study Day/(dose number)			0/(1)	7/(2)	14/(3)	28/(5)	31-34	56/(9)	59-62	84	105	
Visit Window (days)		+7	0	0	±2	±3		±3		±3	±3	
Administrative												
Informed consent	X											
Diabetes medical history/therapy	X											
Inclusion/exclusion	X	X	X									
Preexisting conditions	X											
Randomization			X									
IWRS	X	X	X	X	X	X		X		X	X	X
BG meter/supplies, if needed		X										
BG meter, instructions		X										
Diet, exercise, BG counseling		X										
Study diary, dispense		X	X	X	X	X		X		X		
Review patient diaries for BG values, AEs, hypoglycemic or hyperglycemic events		X	X	X	X	X		X		X	X	X
Subcutaneous injection training		X	X	X	X	X		X				
Study drug and injection supplies, dispense			X	X	X	X		X				
Health habits (alcohol use, tobacco use current/past)	X											
Patient returns study drug vials						X		X		X		
Study drug, assess compliance			X	X	X	X		X		X		
Patient Demographics												
Age	X											
Gender	X											
Race/ethnicity	X											

Study Phase	Screen	Lead-In	Randomize	Treatment							Follow-Up	Early Term.
				4	5	6	7T ^a	8	9T ^a	10 ^b		
Visit	1	2	3	4	5	6	7T ^a	8	9T ^a	10 ^b	801 ^d	ET
Week of Treatment	-2	-1	0	1	2	4	4	8	8	12	(15)	
Study Day/(dose number)			0/(1)	7/(2)	14/(3)	28/(5)	31-34	56/(9)	59-62	84	105	
Visit Window (days)		+7	0	0	±2	±3		±3		±3	±3	
Clinical Variables												
Physical examination ^c	X											
Height	X											
Weight	X		X			X		X		X	X	X
Waist circumference	X		X			X		X		X	X	X
Vital signs (BP and PR)	X	X	X	X	X	X		X		X	X	X
Antidiabetic medication	X	X	X	X	X	X		X		X	X	X
Concomitant medication	X	X	X	X	X	X		X		X	X	X
Other												
ECG ^e	X ^e		X			X		X		X	X	X ^e
Evaluation of injection site reactions			X	X	X	X		X		X	X	X
Collect AEs	X	X	X	X	X	X		X		X	X	X
Diagnostics (Safety)												
Screening laboratory tests ^f	X											
Pregnancy test ^g	X		X ^g									
FSH ^h	X											
Chemistry panel	X		X							X	X	X
Lipid panel	X		X							X	X	X
Lipase and amylase	X		X			X		X		X	X	X
eGFR	X											
Hematology	X		X							X	X	X
Urinalysis	X		X							X	X	X

Study Phase	Screen	Lead-In	Randomize	Treatment							Follow-Up	Early Term.
				4	5	6	7T ^a	8	9T ^a	10 ^b		
Visit	1	2	3	4	5	6	7T ^a	8	9T ^a	10 ^b	801 ^d	ET
Week of Treatment	-2	-1	0	1	2	4	4	8	8	12	(15)	
Study Day/(dose number)			0/(1)	7/(2)	14/(3)	28/(5)	31-34	56/(9)	59-62	84	105	
Visit Window (days)		+7	0	0	±2	±3		±3		±3	±3	
Diagnostics (Efficacy)												
Calcitonin	X									X		X

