HbA1c	X		X			X		X		X	X	X
Fasting glucose	X		X			X		X		X	X	X
Total and active GLP-1/GIP			X			X		X		X	X	
7-point SMBG			X ¹							X ^j		
PK ^k						X		X		X	X	X
Immunogenicity			X			X		X		X	X ¹	X
Nonpharmacogenetic stored samples			X							X		

Abbreviations: AE = adverse event; BG = blood glucose; BP = blood pressure; ECG = electrocardiogram; eGFR = estimated glomerular filtration rate; ET = Early Termination; FSH = follicle-stimulating hormone; GLP-1 = glucagon-like peptide-1; GIP = glucose-dependent insulinotropic peptide; HbA1c = hemoglobin A1c; IWRS = interactive web response system; LH = luteinizing hormone; PK = pharmacokinetics; PR = pulse rate; SMBG = self-monitoring of blood glucose; T = telephone visit; TE = treatment emergent; Term. = termination.

- a Telephone visits occur during the week following a dose escalation and should be done 3 to 6 days after a site visit for dose escalation and administration. At telephone visits, the sites should call the patient, ask how the patient is, and ask whether the patient would like to come to the site for assistance with the next study drug dilution and administration. Sites should also remind patients to write down any AEs in their diaries at the telephone visits (as well as at all site visits).
- b Visit should occur approximately 1 week after the last dose (Dose 12).
- c Additional physical examinations may be performed throughout the study if determined necessary due to patient symptoms.
- d Visit should occur 4 weeks after the last dose of study drug or 3 weeks after Visit 10.
- e ECGs should be collected prior to all blood draws and study drug administrations. Local ECGs will be collected for screening (Visit 1) and Early Termination. Centralized ECGs, collected in supine position and in triplicate, should be collected for all other designated visits.
- f Screening laboratory tests include serum hepatitis B surface Ag, hepatitis C antibody (Ab), and human immunodeficiency virus (HIV) Ab tests for all patients (see Appendix 2).
- g Serum pregnancy test will be performed by central laboratory at Visit 1 for women of child-bearing potential. For the remainder of the study, a urine pregnancy test may be performed at the investigator's discretion if pregnancy is suspected during the study (local laboratory). A urine pregnancy test (local) should be given to all women of child-bearing potential at Visit 3 prior to administration of first dose of study drug to confirm lack of pregnancy.

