9.4.2. Vital Signs

Sitting BP and PR will be measured using standardized equipment provided by the sponsor. Vital sign measurements should be taken before obtaining an ECG tracing and before collection of blood samples for laboratory testing, at visits where required (see Section 2). The participant should be required to sit quietly for 5 minutes before vital sign measurements are taken. An appropriately sized cuff (cuff bladder encircling at least 80% of the arm) should be used to ensure the accuracy of BP measurements. The arm used for the BP measurement should be supported at heart level. At Visit 1 (screening), to determine which arm should be used to collect BP and PR throughout the study, BP and PR will be measured once in each arm, and the arm that had the higher systolic BP should be used to collect all 3 measurements of both BP and PR at all study visits. For each parameter (PR, systolic BP, and diastolic BP), 3 measurements will be taken using the same arm; the recordings should be taken at least 1 minute apart, and each

measurement of sitting PR and BP will be recorded in the eCRF. Any AE related to changes in BP and PR should be reported.

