6.1. General Considerations

Statistical analysis of this study will be the responsibility of Lilly or its designee. Any change to the statistical methods described in the protocol will require an amendment only if it changes a principal feature of the protocol. Any other change to the statistical analyses and the justification for the change will be described in the SAP and/or clinical study report (CSR). Additional exploratory analyses of data may be conducted, as deemed appropriate, without further changes made to the protocol or SAP even after the database lock (DBL).

No adjustments for multiplicity will be performed.

All tests of treatment effects will be conducted at a 2-sided alpha level of 0.05 and/or 2-sided 95% confidence interval (CI) unless otherwise stated. This is different from what is stated in the protocol.

The baseline visit will be Visit 3. For all variables, if baseline data are not available or are missing, the last nonmissing measurement taken prior to Visit 3 will be used for the baseline measurement.

All efficacy and safety data will be summarized by each treatment group at each scheduled visit unless otherwise indicated. Imputed data may be applied in model-based data analysis, but will not be used in data listing.

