6.1.1. Analysis of Repeated Measures

The mixed model for repeated measures (MMRM) using restricted maximum likelihood (REML) will be used to fit change from baseline values at all scheduled visits. The model will include the treatment group, strata (that is, baseline HbA1c category, baseline BMI category, and metformin use [yes, no]), visit, and treatment-by-visit interaction as fixed effects, baseline value of the dependent variable as a covariate, and patient as a random effect. If the analysis is on the primary endpoint, baseline HbA1c category will not be included in the model in addition to the continuous covariate of baseline HbA1c. To model the covariance structure within patients, the unstructured covariance matrix will be selected initially. If the unstructured covariance structure leads to nonconvergence, the following covariance structures will be tested in order:

- Toeplitz with heterogeneity
- autoregressive with heterogeneity
- compound symmetry with heterogeneous variances
- Toeplitz
- autoregressive
- compound symmetry without heterogeneous variances
- compound symmetry

The first covariance structure that converges will be used.

Kenward-Roger method will be used to estimate the denominator degrees of freedom and the restricted maximum likelihood approach will be used to determine the model estimates.

The MMRM model will present least squares (LS) mean estimates for each scheduled week by treatment group and 2-sided 95% CIs for mean changes from baseline within and (when warranted) between treatments. T-statistics corresponding to the Type III sums of squares for the differences in the LS means will be used to obtain p-values for treatment group comparisons.

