6.10.1. Vital Signs

Vital sign measurements (that is, systolic blood pressure [SBP] and diastolic blood pressure [DBP] in mmHg and pulse rate [PR] in beats/minute) will be collected according to the Study Schedule of Events ([Appendix 1](#)). The average 3 measurements for BP and PR will be calculated and analyzed; however, values obtained from fewer than 3 measurements will also be included in summaries and analyses.

Descriptive statistics will be provided by treatment arm for change from baseline at each visit for SBP, DBP, PR. Figures will display LS mean values for change from baseline at each visit for the LY3298176 groups versus placebo.

The above measures will be analyzed using the MMRM-based model described in Section [6.1.1](#). The dependent variable will be the postbaseline change from baseline value for the applicable measure.

The frequency and percentage of patients showing vital sign results in each of the categories specified in [Table 6.4](#) will also be summarized by treatment and visit.

Table 6.4. Vital Sign Summary Categories

Vital Sign Measure	Unit	Low	High
Systolic Blood Pressure	mmHg	≤ 90 and decrease ≥ 20	≥ 160 and increase ≥ 20
Diastolic Blood Pressure	mmHg	≤ 50 and decrease ≥ 10	≥ 100 and increase ≥ 10
Pulse Rate	bpm	< 50 and decrease ≥ 15	> 100 and increase ≥ 15

Abbreviations: bpm = beats per minute.

All vital signs and physical characteristics measurements will be listed.

For pulse rate, a longitudinal dose-response model with titration may be performed, if deemed necessary.

6.10.2. High-Density Lipoprotein Cholesterol, Total Cholesterol, Triglycerides, and Low-Density Lipoprotein Cholesterol

Change from baseline in high-density lipoprotein cholesterol (HDL-C), total cholesterol, triglycerides, and low-density lipoprotein cholesterol (LDL-C) will be analyzed using the ANCOVA model similar to the model used for the supportive analysis on the primary endpoint. The model will include strata (baseline HbA1c category, baseline BMI category, metformin use [yes, no]), treatment, as fixed effects, the applicable baseline measurement as a covariate. The dependent variable will be the postbaseline change from baseline value for the applicable measure.

Descriptive summaries will also be presented.

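### Blood pressure and pulse are taken at three pre-dose visits, but the vital-sign model adjusts for Visit 3 only, so its valid contrasts may be somewhat less precise than the collected data allow

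*Protocol*

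**What the plan says.** The Schedule of Activities (Protocol Section 2, repeated in SAP Appendix 1) marks blood pressure and pulse at Visit 1 (week -2), Visit 2 (week -1) and Visit 3 (week 0). The Visit 3 reading is also pre-dose. Protocol 9.4.2 says "Vital sign measurements should be taken before obtaining an ECG tracing and before collection of blood samples for laboratory testing", and footnote e of the Schedule says "ECGs should be collected prior to all blood draws and study drug administrations". Within a visit, for each parameter, "3 measurements will be taken using the same arm" (Protocol 9.4.2), and SAP 6.10.1 analyses their average.

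For the analysis, Protocol 10.3.4.3 says "Vital signs will be analyzed using a similar MMRM-based model as for the primary analysis". SAP 6.10.1 says "The above measures will be analyzed using the MMRM-based model described in Section" 6.1.1, and that section lists "baseline value of the dependent variable as a covariate". SAP 6.1 says "The baseline visit will be Visit 3" and falls back on an earlier value only if the Visit 3 value is missing. This agrees with Protocol 10.3.1, which takes the last scheduled value before randomization. Neither document averages across visits or enters the Visit 1 and Visit 2 values as covariates.

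**The concern.** Averaging three readings at one visit reduces error within that visit. It does not remove variation from one day to another. A patient's usual level is better estimated from several days than from one, and a better pre-dose predictor of the Week 12 value leaves less residual variance in the comparison with placebo. Two further pre-dose days are already in the database and play no part in the model for a patient with a Visit 3 value.

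What is at stake is the width of the intervals for systolic pressure, diastolic pressure and pulse. SAP 6.10 and 6.10.1 foresee model-based comparisons with placebo and least-squares mean figures for these measures. The sample size was set on HbA1c, with about 20 completers per arm.

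**Working it through.** **The plan's own figure.** The only power statement (Protocol 10.1, SAP 5.3) is for HbA1c: SD 1.1, 20 per arm, smallest assumed difference 1.4 - 0.2 = 1.2. The standard error is 1.1 × √(2/20) = 0.348, and 1.2/0.348 = 3.45. By the normal approximation, power is 93.2% at two-sided 0.05 (SAP) and 98.5% at one-sided 0.1 (protocol). The stated figure of at least 90% holds, and 80/0.87 = 92 matches the number randomized. No SD, correlation, difference or power is given for vital signs, so none can be reproduced.

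**Inputs for the check (assumed).** Scale each visit's value to variance 1. Let r be the correlation between any two pre-dose visits (0.6 to 0.8), c the correlation of Visit 3 with Week 12 (0.5 to 0.6), and d the amount by which Visits 1 and 2 correlate less with Week 12 than Visit 3 does (0, 0.05 or 0.10).

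**Formulas.** With the baseline as covariate, analysing change from Visit 3 gives the same treatment contrast as analysing the Week 12 value.
- Residual variance with Visit 3 only: 1 - c².
- The mean of Visits 1 and 2 has variance (1 + r)/2, covariance r with Visit 3 and covariance c - d with Week 12.
- Extra variance explained by adding it: (c - d - rc)² / [(1 + r)/2 - r²].
- Ratio of standard errors: the square root of the ratio of residual variances.

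**Central case, r = 0.7, c = 0.6.** Visit 3 only leaves 1 - 0.36 = 0.64. The denominator is 0.85 - 0.49 = 0.36.
- d = 0: 0.18²/0.36 = 0.090, so 0.64 becomes 0.550, a cut of 14%.
- d = 0.05: 0.13²/0.36 = 0.047, so 0.64 becomes 0.593, a cut of 7%.
- d = 0.10: 0.08²/0.36 = 0.018, so 0.64 becomes 0.622, a cut of 3%.

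**Ends of the range.** The largest gain is at r = 0.6, c = 0.6 (residual 0.64, denominator 0.80 - 0.36 = 0.44). The smallest is at r = 0.8, c = 0.5 (residual 0.75, denominator 0.90 - 0.64 = 0.26).

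| d | Extra explained, smallest | Extra explained, largest | Cut in residual variance | Cut in standard error |
|---|---|---|---|---|
| 0 | 0.10²/0.26 = 0.0385 | 0.24²/0.44 = 0.1309 | 5.1% to 20.5% | 2.6% to 10.8% |
| 0.05 | 0.05²/0.26 = 0.0096 | 0.19²/0.44 = 0.0820 | 1.3% to 12.8% | 0.6% to 6.6% |
| 0.10 | 0²/0.26 = 0 | 0.14²/0.44 = 0.0445 | 0% to 7.0% | 0% to 3.5% |

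**Charge for the extra term.** With 80 evaluable patients, four arms, three two-level strata and one baseline covariate leave 80 - 4 - 3 - 1 = 72 degrees of freedom. One more covariate costs roughly 1/72, or 1.4%, of variance. At the weakest corner of the table this cancels the gain or slightly exceeds it; elsewhere it is small.

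The calculation treats Week 12 as a single outcome. The MMRM also uses the other post-dose visits, so these figures are approximate for it.

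**The case against.** The strongest objection is that Visits 1 and 2 are probably not as good predictors as Visit 3, and the documents give reasons.
- Protocol 7.2.2 requires fasting only before visits with fasting samples or weight. Visit 2 has neither, whereas Visits 3 and 10 have both, so Visit 2 readings may be non-fasting.
- Visit 1 blood pressure is the eligibility reading, with patients at or above 160 systolic or 95 diastolic excluded (exclusion 23). Truncation tends to weaken its correlation with later values.
- Visit 1 is also where the arm for later readings is chosen (Protocol 9.4.2).
- Both visits lie further from Week 12. If correlation decayed purely with time (first-order autoregressive, with no stable patient level and no visit-level noise), Visit 3 would carry all the information and the gain would be zero.

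This stands, and it is why the table goes beyond d = 0. It limits the size of the gain but introduces no bias. The earlier values are pre-randomization covariates, and as a separate term they get their own coefficient, so equal means or spread need not be assumed.

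It is also fair to say that a single prespecified baseline, already a mean of three readings, is a sound model. SAP 6.1 allows further exploratory analyses, so the adjusted model could be run without a change to the plan, though not as a prespecified analysis.

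A reader might go further in three ways that the documents do not support.
- **Pulse singled out.** The MMRM and the least-squares mean figures apply equally to both pressures. Only the optional dose-response model is specific to pulse.
- **A power shortfall.** Vital signs have no stated hypothesis, difference or power target. Safety analyses use all available data in treated patients (SAP 6.3), with about 23 per arm randomized, so 20 per arm may be conservative.
- **The same change for fasting glucose and waist circumference.** Each has only one earlier value (Visit 1). The gain may be negligible for glucose and has not been shown for waist.

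**Conclusion.** The point holds as a modest one about efficiency. Three pre-dose visits are measured and one enters the vital-sign model. The planned contrasts remain valid and unbiased under randomization; a reader who inferred a biased or defective analysis would be going beyond the documents.

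Across the assumed correlations, the standard error would fall by between nearly nothing and about 11%. The upper end requires Visits 1 and 2 to predict Week 12 as well as Visit 3 does, and the documents give reason to doubt that. In the central case the variance cut is 14%, 7% or 3%, depending on how much weaker the earlier visits are. All of this rests on correlations the documents do not supply. No sample-size figure is affected. It is an optional improvement.

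**What to change.** In SAP 6.10.1, keep change from Visit 3 as the response, the Visit 3 value as covariate and Visit 3 as the reference for Table 6.4. Add one sentence prespecifying the mean of the available Visit 1 and Visit 2 values as a second continuous covariate in the MMRM for systolic pressure, diastolic pressure and pulse. The sentence should also say what is used when Visit 2 has stood in for a missing Visit 3 value. It should be in place before unblinding, so that the choice of model cannot depend on the results.

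The cost is that sentence and one degree of freedom. No new data, visits or procedures are needed, and no other model needs to change.
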